#### STUDY PROTOCOL

#### Study Design

The trial was conducted between 01AUG 2016 and 25FEB 2020 at 6 clinical sites: five University academic medical sites and one University active-duty military hospital. The trial consisted of ten-week, randomized, double-blind, placebo-controlled administration of losartan or placebo. Eligible participants were randomized in a 1:1 ratio based on a randomly permuted block design stratified by site. Participants were prescribed 25 mg of active drug or placebo at Week 0 and then flexibly uptitrated (as tolerated) to 50 mg by Week 2, 75 mg by Week 4, and then 100 mg at Week 6. If significant side effects were encountered, the dosage could be held or reduced to a minimum of 25 mg and held stable at Week 6. Participants unable to tolerate the 25 mg dose were withdrawn from the study.

Losartan and placebo were prescribed as identical capsules, with the losartan overencapsulated. Randomization lists were prepared by the biostatistics analytical team (led by SJ) and distributed to research pharmacies at the sites who dispensed the drug. Only the biostatistics team had access to the treatment assignment codes.

#### Study Participants

Potential subjects participated in informed consent procedures approved by Institutional Review Boards for each performance site and the Department of Defense Human Research Protection Office (HRPO). A Data Safety Monitoring Board (DSMB) oversaw safety and progress of the study. To be included in the trial, veteran or civilian women and men, aged 18-70 years were required to meet past-month criteria for posttraumatic stress disorder (PTSD) according to DSM-5. Participants were required to have a CAPS-5 score of  $\geq$  25 at screening in order to enter the trial.

Exclusion criteria were: 1) current, imminent risk of suicide (as assessed by the C-SSRS (23)), 2) active psychosis, 3) moderate or severe DSM-5 alcohol or other substance use disorder in the past 3 months, 4) unable to attend regular appointments, 5) prior intolerance of or allergy to losartan or other ARBs, 6) medical illness likely to result in imminent hospitalization or for which treatments are contraindicated (based on lab results, medical history and physical exam) (e.g., systolic blood pressure < 90 mm Hg), 7) serious cognitive impairment (as evidenced by cognitive impairment felt likely to interfere with the ability to participate meaningfully in the study); traumatic brain injury was not excluded unless there was serious cognitive impairment, 8) concurrent ACE Inhibitors or ARBs, 9) concurrent antidepressants or antipsychotics, and 10) currently pregnant or trying to become pregnant, or of childbearing potential and unwilling to use a proven method of birth control. Potential participants were required to be off of all antidepressants for a minimum of 2 weeks (6 weeks for fluoxetine) prior to randomization; only 2 participants had been on SSRIs prior to entering the study. Sleep agents (e.g., trazodone < 200 mg; eszopiclone; zolpidem) were allowed as long as the dose had been stable for at least 2 weeks; 14 patients used p.r.n. sleep aids during the study. Participation in a trauma-focused psychotherapy during the trial was prohibited. Participation in other psychotherapeutic modalities maintained for 3 months before and during the trial was permitted; 2 patients were on long-term supportive therapy during the study.

#### Study Procedures

All intakes and interview measures were completed by trained study personnel qualified to conduct the intake assessment. CAPS-5 training and certification was conducted (by [name] PhD) at the start of the study and yearly recalibration assessment reviews took place at each site. At intake, a standardized past and current medical history with review of symptoms (including allergies to losartan, other ARBs, or any other medications) was obtained. The study physician also conducted a screening medical examination that included determination of standing and sitting blood pressure. Blood was drawn for renal and liver function tests, urine for drug screen, and a baseline EKG. If the patient was a woman of childbearing potential a urine pregnancy test was also done.

#### Study Assessments

Study assessments occured at baseline week (week 0) and weeks 1, 2, 4, 6, 8 and 10. These assessments included interview and self report measures of symptoms and function, as well as evaluation of adverse events and assessment of standing and sitting blood pressure. The primary endpoint was at 10 weeks and the primary outcome measure was the Clinician Administered PTSD Scale for DSM-5 (CAPS-5; (24)), the gold standard in PTSD assessment. The CAPS-5 past-month was administered at intake and the past-week version re-administered at Weeks 0 (baseline), 4, 8 and 10 week endpoint (or earlier endpoint if the subject discontinued early from the study). Key secondary measures were the PTSD Checklist for DSM-5 (PCL-5; (25)) and the Clinical Global Impressions of Improvement Scale (CGI-I; (26)), and the Patient Health Questionnaire-9 (PHQ-9; (27)) for depressive symptoms.

#### Genotyping and Genetic Analysis

DNA was collected from salivary samples using the Oragene OG-500 salivary DNA collection Kit. DNA from all participants was extracted using Qiagen extraction kits, and quantifed by gel electrophoresis using Quantity One (BioRad, Hercules, CA) and then normalized. Taqman reactions were performed using Taqman SNP Genotyping Assays along with Taqman Genotyping Master Mix (Applied Biosystems Inc., Foster City, CA). rs4311 alleles were discerned using the 7900HT Fast Real-Time PCR system.

## STATISTICAL ANALYSIS PLAN

### Statistical Methods

The primary outcome (CAPS-5) was analyzed using an MMRM (mixed model repeated measures) approach based on a modified intent-to-treat (mITT) population, defined as randomized subjects who initiated treatment and had both a baseline and at least one postbaseline outcome score during the blinded phase of the study (Week 10). Participants from the mITT population who were included in the MMRM model also required both a baseline and at least one post-baseline CAPS-5 score. The model included as the dependent variable change from baseline in CAPS-5 total score at each post-baseline visit (Weeks 4, 8 and 10). Independent variables in the MMRM model included treatment, visit, treatment-by-visit interaction, and baseline CAPS-5 total. Visit was treated as a categorical variable. Unstructured variance-covariance structure was used. This same analysis was also repeated on the per protocol population, defined as as all eligible subjects for whom the 10-week assessments for the primary analysis were available and who were dispensed at least 50mg of the protocol prescribed medication at the 6-week time point. Descriptive analyses were performed to compare baseline data between treatment groups. Categorical variables were evaluated using Fisher's exact test. Continuous variables were analyzed with Wilcoxon's rank sum test. Safety data were summarized overall and by treatment groups for the blinded and extended phases of the study. Fisher's exact test was used to compare the number of subjects between groups who experienced any adverse events.

The study was a priori powered assuming 10% attrition and an alpha set to 0.05 using a twosided, two-sample t-test. Based on a sample size of 160 subjects to have an evaluable sample size of 144 (72 per arm), we could detect with 80% power a standardized change score between the groups of 47%. All analyses are based on the modified intent-to-treat (mITT) sample unless otherwise specified.

Analogous methods to the primary analysis were used for the other continuous secondary outcomes. The categorical secondary outcome, treatment response status, (response defined as a score of 1 ["Much Improved"] or 2 ["Improved"] on the CGI-I) was analyzed using a generalized estimating equation (GEE) model for binary data. The model included the binary responder status at Weeks 1, 2, 4, 6, 8 and 10 as the dependent variable; treatment, visit and the treatment-by-visit interaction as independent variables. Statistical analyses were performed using R version 3.5.2 (http://www.r-project.org).

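### Randomisation was stratified by six sites, but the CAPS-5 MMRM and the other linear models leave site out; if site predicts outcome beyond baseline, the test is conservative and some precision is lost

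*Combined protocol and SAP*

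**What the plan says.** Study Design in the combined protocol and SAP states the allocation: "Eligible participants were randomized in a 1:1 ratio based on a randomly permuted block design stratified by site". It also gives the number of sites: "The trial was conducted between 01AUG 2016 and 25FEB 2020 at 6 clinical sites".

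Statistical Methods lists the terms of the primary model: "Independent variables in the MMRM model included treatment, visit, treatment-by-visit interaction, and baseline CAPS-5 total". The outcome is change in CAPS-5 at Weeks 4, 8 and 10, with visit categorical and an unstructured covariance. Site is not in the list.

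Two statements carry the same specification further: "This same analysis was also repeated on the per protocol population" and "Analogous methods to the primary analysis were used for the other continuous secondary outcomes". From Study Assessments, the latter take in PCL-5 and "Patient Health Questionnaire-9 (PHQ-9; (27)) for depressive symptoms". Nowhere is site entered as a fixed or random effect, its absence explained, or a site-adjusted analysis planned.

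The power statement rests on a two-sided two-sample t-test at 0.05, with 160 randomised, 144 evaluable (72 per arm) and a standardised difference of 0.47.

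**The concern.** Blocking within site makes the arms nearly equal in size at each site, so differences between sites largely cancel out of the treatment contrast. A linear model without site does not know this. It leaves between-site variance in the residual and counts it as error. If site predicts change in CAPS-5 after baseline is accounted for, the model-based standard error then exceeds the true one.

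What is at stake is efficiency and an accurate standard error. A reader of the result cannot tell whether the interval is wider than the design warrants. The randomisation has already made the extra precision available, and the analysis does not collect it.

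**Working it through.** **Plan's own figure.** With 72 per arm and SD 1, the SE is √(2/72) = 0.1667 and the noncentrality is 0.47/0.1667 = 2.82. The exact t-test power on 142 df is 79.98%, and 144/0.9 = 160. The stated design reproduces.

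**Assumed input.** Let ρ be site's share of Week 10 residual variance. The documents do not give it, so 0, 2, 5 and 10% are used. Total residual SD is 1, with no credit for baseline.

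**Upper bound: exact balance within site, all Week 10 site variance removed.**

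- Reported SE without site: √(2/72). True SE: √(2/72) × √(1-ρ).
- Without site, the effective critical value is k = t(0.975, 142)/√(1-ρ). True alpha is 2·P(t142 > k). Power is from the noncentral t on 142 df with noncentrality 2.82/√(1-ρ).
- With site: the same noncentrality, 142 - 5 = 137 df, critical value t(0.975, 137).

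Example at ρ = 5%: k = 1.977/0.9747 = 2.028, and the noncentrality is 2.82/0.9747 = 2.893.

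| ρ | SE overstated | True alpha without site | Power without site | Power with site | Change (points) |
|---|---|---|---|---|---|
| 0% | 0% | 5.0% | 79.98% | 79.96% | -0.02 |
| 2% | 1.0% | 4.8% | 80.22% | 80.75% | +0.53 |
| 5% | 2.6% | 4.4% | 80.58% | 81.94% | +1.36 |
| 10% | 5.4% | 3.9% | 81.21% | 83.93% | +2.72 |

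**Imperfect balance.** Simulations of a Week 10 linear model assumed 160 randomised, blocks of 4, about 10% random loss, and equal or unequal sites. Across two sets of runs, adding site changed power by -0.2 to -0.5 points at ρ = 0, by +0.5 to +1.3 at 5% and by +1.9 to +2.9 at 10%. One set also covered 2%, with +0.2 to +0.4 and a Monte Carlo SE of about 0.2.

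**Site main effect only.** In an MMRM, a single site effect is a weighted average over the three visits. Let s be the fraction of site variance shared across visits.

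- *Equal variances and equal correlations.* The weights are 1/3 each and the Week 10 site variance left is ρ(1-s)·2/3. At ρ = 2/5/10% the gain is 0.35/0.90/1.82 points for s = 0.5 and 0.16/0.44/0.91 for s = 0.
- *Variance growing over visits* (assumed SDs 0.7/0.9/1.0, correlation 0.6, site SDs in proportion). The GLS weights V⁻¹1/(1ᵀV⁻¹1) are 0.771/0.189/0.040. The fraction of Week 10 site variance left is:
  - s = 1: (1 - 0.771×0.7 - 0.189×0.9 - 0.040)² = 0.06
  - s = 0: 0.771²×0.49 + 0.189²×0.81 + 0.960² = 1.24
  - s = 0.5: the average of these, 0.65

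In this second case, 4,000 simulated trials per scenario gave about +0.1 and +0.7 points at 5 and 10% for s = 0.5, and about -0.2 and -0.5 for s = 0.

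**Break-even share.** This is a cost of about 0.2 points (imbalance, no site effect) divided by the gain per 1% of ρ.

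- Fully shared: 0.2/(0.53/2) = 0.75%
- Half shared, equal variances: 0.2/(0.35/2) = 1.1%
- None shared, equal variances: 0.2/(0.16/2) = 2.5%

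With growing variances it is higher, and where the gain is negative there is no break-even.

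**The case against.** The other side can fairly say that all the harm is conditional. Every non-zero gain rests on an assumed site share. Baseline CAPS-5 is already in the model, and Study Procedures describes CAPS-5 training and certification, after which "yearly recalibration assessment reviews took place at each site". Residual site variance may be small or nil. At 2% with imperfect balance, the gain is barely distinguishable from simulation error. This stands: it limits the size of the point but does not explain the omission.

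It can also be said that adding only a site main effect may not help. This stands too. The unstructured covariance allows variance to grow over visits, and the weights then shift towards Week 4. A break-even of 0.7-0.8% is therefore the best case, and the site-by-visit term belongs in the adjusted model.

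A third argument is that the trial is described as completed, so an added analysis only supplies a second p-value. This stands in part. The planned result must remain the planned result. A labelled companion analysis still shows whether the reported standard error is too large.

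A reader might infer more than the documents support: that leaving out a stratification factor biases the treatment effect, inflates type I error or undermines the 80% power. It does none of these. The imbalance that would cause bias is what stratified blocks prevent, the error in the standard error is on the cautious side, and the power calculation was a plain t-test that took no credit for stratification. Nor do the documents show that site matters in this trial.

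**Conclusion.** The mismatch between design and analysis is clear in the text, and the direction of its effect is certain if site predicts outcome: a conservative test and an interval that is too wide. The size is uncertain and modest, at most about 2.7 points of power and a true alpha of 3.9% at an assumed 10% site share, and nothing material if the share is zero. These bounds assume exact within-site balance and removal of all Week 10 site variance. No single break-even share applies: it is 0.7-0.8% at best, and about 1.1-2.5% or higher when site effects are partly shared or not shared across visits.

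The figures concern CAPS-5 in the mITT population. The omission extends to the per-protocol, PCL-5 and PHQ-9 models, but the benefit there is not quantified, and within-site balance may be poorer in a per-protocol set selected after randomisation. The CGI-I GEE also lists no site term. It is outside this point, because the argument is for linear models. The change is worth making but not critical.

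**What to change.** Keep the planned MMRM as the reported primary analysis. Add, labelled as site-adjusted, a CAPS-5 MMRM in the mITT population with site and site-by-visit as fixed effects. Pool very small sites by a rule chosen without reference to treatment results. Do the same for the per-protocol CAPS-5 model and for PCL-5 and PHQ-9.

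The cost is 5 site parameters plus 5 × 2 = 10 site-by-visit parameters over three visits, which is about five degrees of freedom at Week 10 out of about 140. If site has no effect, power falls by about 0.02 points under exact balance and by a few tenths of a point under realistic imbalance. No new data or patients are needed.

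### The primary MMRM adjusts for the Week 0 CAPS-5 but not for the intake CAPS-5 that is also available before randomisation: a modest missed gain in precision in an otherwise valid model

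*Combined protocol and SAP*

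**What the plan says.** Under Study Assessments, the primary scale is given twice before treatment: "The CAPS-5 past-month was administered at intake and the past-week version re-administered at Weeks 0 (baseline), 4, 8 and 10 week endpoint". Week 0 is therefore the baseline.

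Under Study Participants, the earlier score is an entry requirement: "Participants were required to have a CAPS-5 score of" at least "25 at screening in order to enter the trial". I read the screening score and the past-month intake score as the same administration, because no other CAPS-5 before Week 0 is described.

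Under Statistical Methods, the outcome is defined as follows: "The model included as the dependent variable change from baseline in CAPS-5 total score at each post-baseline visit (Weeks 4, 8 and 10"). The full list of terms is: "Independent variables in the MMRM model included treatment, visit, treatment-by-visit interaction, and baseline CAPS-5 total". The per-protocol analysis repeats this model. No section uses the intake score in an analysis.

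The sample size paragraph of the same section does not rely on covariate adjustment: "The study was a priori powered assuming 10% attrition and an alpha set to 0.05 using a twosided, two-sample t-test".

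**The concern.** A single clinician rating is a noisy measure of a participant's usual severity. If so, a second rating on the same scale can carry information about the Week 10 score that the first lacks. The intake score precedes randomisation, so adjusting for it cannot bias the treatment contrast. It is already collected and, because entry depends on it, should be complete for eligible participants.

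Leaving it out may make the residual variance of the Week 10 contrast somewhat larger than the collected data require, and the confidence interval correspondingly wider. Only efficiency is at stake. The estimand, the type I error rate and the validity of the estimate are unaffected.

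**Working it through.** **1. The plan's own figures.** The inputs, all from Statistical Methods, are 160 randomised, 10% attrition, two-sided alpha 0.05, a two-sample t-test, 80% power and a standardised difference of 0.47.

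- Evaluable: 160 × 0.90 = 144, or 72 per arm.
- Noncentral t with 142 degrees of freedom and noncentrality 0.47 × √(72/2) = 2.82: power 79.98%.
- Difference detectable with 80% power: 0.470.

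The stated design reproduces.

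**2. Formula for the gain.** Let S be the intake score, B the Week 0 score and Y the Week 10 score. With B already in the model, change from B and Y itself give the same treatment contrast, so the residual variance of Y can be used. Adding S multiplies that variance by 1 − p², where p is the partial correlation of S with Y given B:

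p = (r_SY − r_SB × r_BY) / √[(1 − r_SB²)(1 − r_BY²)]

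This treats the Week 10 contrast as a complete-data ANCOVA, an approximation to the MMRM. For power I take 0.47 to be in units of the SD after Week 0 adjustment and recompute at 0.47/√(1 − p²) with 72 per arm.

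**3. Assumed correlations.** The documents give none, so all of these are assumptions.

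| r_SB | r_BY | r_SY | p | Variance ratio | Power |
|---|---|---|---|---|---|
| 0.6 | 0.5 | 0.50 | 0.289 | 0.917 | 83.3% |
| 0.7 | 0.5 | 0.50 | 0.243 | 0.941 | 82.3% |
| 0.6 | 0.5 | 0.45 | 0.217 | 0.953 | 81.8% |
| 0.7 | 0.5 | 0.40 | 0.081 | 0.993 | 80.2% |
| 0.7 | 0.5 | 0.35 | 0 | 1.000 | 80.0% |

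The third row in full: p = (0.45 − 0.6 × 0.5)/√(0.64 × 0.75) = 0.15/0.693 = 0.217, and 1 − 0.217² = 0.953. The last row is pure serial decay: r_SY = 0.7 × 0.5 = 0.35, so Week 0 holds everything that intake could tell and the gain is nil.

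**4. Grid.** I took five evenly spaced values each of r_SB (0.5-0.7), r_BY (0.4-0.6) and the shortfall of r_SY below r_BY (0-0.1), 125 points in all. The residual variance falls by 0.1% to 18.8%, with a median of 4.7%. At 87% of points the fall is 10% or less.

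**5. Effect of the entry cut-off.** Truncating S at 25 weakens its correlations. I simulated a true-severity model with total SD 10, mean 32-40, reliability 0.6-0.8, intake at least 25, and a true change by Week 10 with SD 8-12 (all assumed). The fall in variance was about 3-7%:

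- a 3% fall gives power 81.2% and a confidence interval 1.5% narrower (1 − √0.97);
- a 7% fall gives power 82.8% and an interval 3.6% narrower (1 − √0.93).

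Against 80.0%, that is about 1-3 power points. As evaluable participants out of 144, it is about 4 (144/0.97 − 144) to 11 (144/0.93 − 144).

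**6. Cost.** One more regression coefficient uses one degree of freedom, roughly 1/144 = 0.7% in variance. About 5% of the grid points in step 4 fail to recover it.

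**The case against.** The strongest reply is that nothing in the plan is wrong. The model already adjusts for the score from which change is computed, and leaving out an earlier measurement of the same scale is a legitimate choice. The power statement rests on an unadjusted t-test, so the design never relied on this gain. All of that stands.

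The reply goes on that the size of the gain cannot be established. This also stands. It depends on one unknown, the partial correlation of intake with Week 10 given Week 0. The two scores are not parallel measures either: intake uses a past-month window, whereas Week 0 and the outcome visits use past-week. The simulation allows for the truncation but not for the different window, so its 3-7% may be optimistic.

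Finally, the text describes a trial that ran from August 2016 to February 2020, with its analyses reported in the past tense. Adding a covariate to a completed primary analysis is post hoc. That limits the remedy here but does not make the covariate harmful where it can be pre-specified.

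A reader might infer that the trial gave up substantial power. Equal correlations of 0.5-0.7 among the three scores would cut the variance by 11-17% and take power to 84-87%. That needs intake to predict Week 10 as well as Week 0 does, with no decay over time and no loss from the entry cut-off. The documents offer nothing in support, and the cut-off contradicts the last condition.

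**Conclusion.** The point holds as an optional refinement. The primary MMRM uses one of two CAPS-5 scores available before randomisation, and using both would probably sharpen the Week 10 contrast a little. A fall in residual variance of about 0-10%, typically 3-7%, is a reasonable expectation, or about 1-3 power points at 72 per arm. This rests on assumed correlations and an assumed spread of true change, because the documents supply neither. The gain is nil if Week 0 captures all the prognostic information in the intake score, and the recall window and the cut-off of 25 both reduce it.

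A reader might also take the omission for an error, a source of bias or a flaw in the sample size. The documents support none of these: the model is valid as written, the stated power reproduces, and no section contradicts another on this point.

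**What to change.** Where the analysis can still be pre-specified, as in a successor trial or a re-used SAP, add the intake past-month CAPS-5 total as a second fixed covariate in the primary MMRM and in its per-protocol repeat. Keep the Week 0 past-week score as the baseline for change, so that the estimand is untouched. This takes one model term and one SAP sentence. It needs no new data, and there should be no missing values among eligible participants.

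Where the data are already unblinded or the analysis is complete, as the wording suggests for this trial, leave the primary model unchanged and report the two-covariate model as a sensitivity analysis labelled post hoc. Giving the observed correlations among the intake, Week 0 and Week 10 scores beside it would settle the size of the gain.

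The cost is one degree of freedom (about 0.7%), and post hoc status if the term is added after unblinding.

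### The only between-group adverse-event test defaults to the mITT sample, so it leaves out treated subjects with no post-baseline score, and it states no event window although an undefined extended phase is mentioned

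*Combined protocol and SAP*

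**What the plan says.** Three statements in the SAP's Statistical Methods section bear on the safety comparison.

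- The test: "Fisher's exact test was used to compare the number of subjects between groups who experienced any adverse events". It is the only between-group adverse-event test in the document, and it names neither a population nor a period.
- The sentence just before it: "Safety data were summarized overall and by treatment groups for the blinded and extended phases of the study". This is the only mention of an extended phase. Its treatment, blinding, length, entry rule and event collection are not described.
- The default population: "All analyses are based on the modified intent-to-treat (mITT) sample unless otherwise specified". Membership of mITT requires starting treatment, a baseline score and "at least one postbaseline outcome score during the blinded phase of the study (Week 10").

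Two protocol sections give the setting. Study Design says: "The trial consisted of ten-week, randomized, double-blind, placebo-controlled administration of losartan or placebo". Study Assessments says: "Study assessments occured at baseline week (week 0) and weeks 1, 2, 4, 6, 8 and 10", and lists among the assessments "as well as evaluation of adverse events and assessment of standing and sitting blood pressure". No later visit is listed.

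**The concern.** **Population.** A safety comparison should include everyone exposed to study drug. The mITT rule depends on having an outcome score, so a subject who took a dose and stopped before any score drops out of both numerator and denominator. Stopping that early may itself be due to an adverse event, so the exclusion need not be unrelated to what is being tested.

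**Window.** The test counts subjects with any event, straight after a sentence that covers two phases. One analyst could count events to Week 10 and another could count events over both phases. Both could claim to follow the plan, and they could report different p-values. Only the ten-week phase is described as a randomised, double-blind comparison, so the p-value should not depend on a phase that the plan does not define.

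What is at stake is the interpretation of the single formal safety comparison. The primary efficacy analysis is not affected.

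**Working it through.** **The plan's own figure.** Statistical Methods gives 160 randomised, 10% attrition, 144 evaluable (72 per arm), and 80% power at two-sided 0.05 for a standardised difference of 0.47. Check: 160 × 0.90 = 144, and the noncentral t-test with 72 per arm and 0.47 gives power 79.98%. The figure reproduces, and the present point does not depend on it. The document gives no adverse-event rate and no power for the safety test, so every rate below is an assumption.

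**Population.** Suppose an arm has n treated subjects, x of them with an event, and the mITT rule removes k subjects who all had an event. The rate moves from x/n to (x − k)/(n − k), a fall of k(n − x)/[n(n − k)]. Take n = 160/2 = 80, assuming all were dosed, and k = 1:

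- Losartan at an assumed 65%: 52/80 becomes 51/79 = 64.56%, a fall of 0.44 points.
- Placebo at an assumed 45%: 36/80 becomes 35/79 = 44.30%, a fall of 0.70 points.

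Each lost subject moves an arm by less than one point. Losses from losartan alone narrow the difference and losses from placebo alone widen it. One from each arm gives 64.56 − 44.30 = 20.26 points, slightly more than the true 20. The direction cannot be known without the counts by arm.

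**Window, dilution.** Let p be the blinded-phase event rate, s the share of event-free subjects who enter the extension, and q the first-event rate among those who enter. The rate over both phases is p + (1 − p)·s·q. Power is for the two-sided Fisher test at 0.05 with 72 per arm, summed exactly over both binomial distributions. Blinded phase only, 65% v 45%: 62.9%.

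| Share entering | q, losartan / placebo | Rate over both phases | Power |
|---|---|---|---|
| All | 20% / 30% | 72.0% v 61.5% | 21% |
| All | 30% / 40% | 75.5% v 67.0% | 16% |
| All | 30% / 50% | 75.5% v 72.5% | 5% |
| Half | 20% / 30% | 68.5% v 53.3% | 40% |
| Half | 30% / 40% | 70.3% v 56.0% | 36% |
| Half | 30% / 50% | 70.3% v 58.8% | 24% |
| Quarter | 20% / 30% | 66.8% v 49.1% | 52% |
| Quarter | 30% / 40% | 67.6% v 50.5% | 49% |
| Quarter | 30% / 50% | 67.6% v 51.9% | 42% |

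For example, row 2: 0.65 + 0.35 × 0.30 = 0.755 and 0.45 + 0.55 × 0.40 = 0.670.

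Dilution does not need different extension rates. If all enter and q is the same in both arms, power is 53.5% at q = 10% and 23.8% at q = 50%.

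**Window, false signal.** With 30% in both arms in the blinded phase, the blinded-only test rejects in 3.3% of trials. If all enter and q is 10% v 30%, the rates become 0.30 + 0.70 × 0.10 = 37% and 0.30 + 0.70 × 0.30 = 51%, and rejection rises to 34%. Starting from 50% in both arms, the rates become 55% v 65% and rejection rises from 3.7% to 18%.

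**The case against.** The strongest reply is that silence about a window is not pooling. The sentence before the test splits safety data by phase, Study Design describes a ten-week trial, and the listed adverse-event visits end at Week 10. A blinded-only test is a fair reading, and the by-phase summaries would leave the blinded-phase counts visible in any case. This stands in part: a reader might infer that extended-phase events were counted, and the text does not show that. But the Week 10 limit is attached to the outcome scores that define mITT, not to adverse events. The visit schedule cannot settle the window either, because the SAP says safety data were also summarised for the extended phase.

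A reader might also infer that placebo participants moved to active drug in the extension and that the result is therefore falsely reassuring. The document says nothing about treatment in that phase, and the calculations show that pooling can push the result either way.

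On the population, a reader might infer that everyone who left before the first scheduled post-baseline CAPS-5 at Week 4 is lost. That goes too far. mITT asks for an outcome score, and a CAPS-5 score is an added condition for the MMRM only. CGI-I response is modelled from Week 1, and Study Assessments provides for a CAPS-5 at early discontinuation. The exclusion mainly reaches subjects with no assessment after baseline. It can also be said that the default sentence sits in the sample-size paragraph and was not meant for safety tables. But it covers all analyses unless otherwise specified, and nothing else is specified for safety.

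**Conclusion.** The point holds as a gap in specification with two parts.

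The population part is the firmer one, because it follows from a rule that the plan states: with mITT as the default and no safety set named, the test omits treated subjects without a post-baseline score. The effect is probably small, under one percentage point per lost subject at the assumed rates, and its direction is unknown.

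The window part is an ambiguity, not a demonstrated error. If events from both phases were counted, power for an assumed 65% v 45% difference would fall from 63% to between 5% and 52% over the tabulated scenarios. A rejection rate of 3% to 4% with no blinded-phase difference could rise to 18% to 34%. These figures rest on assumed event rates, assumed entry into the extension and 72 per arm. They show what could happen and do not estimate what did. They do not support a claim that harm was hidden.

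The change is worth making because this is the only formal between-group safety comparison and the repair is cheap.

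**What to change.** In Statistical Methods:

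1. State that the Fisher test is run on all randomised subjects who took at least one dose, as an explicit exception to the mITT default.
2. State that it counts subjects with an adverse event whose onset falls between first dose and Week 10.
3. Define the extended phase: who entered, treatment, blinding, length and how events were collected.
4. Report extended-phase events in a separate descriptive table by treatment actually received, with no between-arm test.
5. Report, by arm, how many treated subjects fall outside mITT.

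The cost is a few sentences, a population flag and a filter on onset date, with no new data. If the test was already limited to the blinded phase, one clarifying sentence settles the window. The downsides are that the safety denominator will differ from the efficacy denominator, and that extended-phase events will not feed the test.
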